2.6.1 Will blood samples be obtained as part of this research study?

* No

*If submitting a protocol for expedited review, it should be clear that the planned blood draws are within the parameters described here: <http://www.hhs.gov/ohrp/policy/expedited98.html> (see Expedited Research Category #2)

If Yes, address the frequency, volume per withdrawal, the total volume per visit, and the qualifications of the individual performing the procedure:

The purpose of the flowchart is to enhance and not replace the detailed description for all research activities in question 2.6.

It is the **responsibility of the PI to ensure consistency of the content within the entire IRB application** which includes all uploaded documents (e.g., sponsor protocol, consent, flow charts).

Study Flow Chart:

Name	Modified Date
Flow Chart	9/1/2015 10:10 AM

View: 2.07 - 2.07(b)

Section 2 - Research Design and Methods

2.7 Will follow-up procedures be performed specifically for research purposes? Follow-up procedures may include phone calls, interviews, biomedical tests or other monitoring procedures.

* Yes

Detailed procedures listed in the textbox below:

The follow up procedures outlined in 2.6. The modified barium swallow, FOIS, and patient weight are routinely performed with clinical patients. Among the procedures in this study the only ones used for research purposes are: the visual analog scale, the EAT-10, and the measurement of tongue strength with the IOPI.

Approximately 8 weeks after the initiation of therapy ("standard" or "standard w/ IOPI") individuals will be asked to complete the VAS and the EAT-10, and the clinician will repeat the FOIS and weight the subjects, once again at their 8-week standard of care clinical follow up visit. 8 weeks is the usual standard of care follow up visit. A modified barium swallow (MBS) test will also be performed as part of standard of care at about the 8 week time point. Finally isometric pressure (tongue strength) will be measured at this point.

View: 2.08

Section 2 - Research Design and Methods

2.8 Does this research study involve the use of any questionnaires, interview or survey instruments?

* Yes

Upload a copy of all materials except for the SCID or KSADS which are on file at the IRB. The use of all instruments must be addressed in question 2.6 and/or question 2.7 (except for an exempt submission where they should be addressed on the appropriate uploaded exempt form).

Name	Modified Date
FOIS scale	9/1/2015 9:15 AM
EAT-10.docx	8/27/2015 4:25 PM
VAS-dysphagia IOPI.docx	8/27/2015 4:28 PM

Previously the name and publisher for commercially available materials were listed in the textbox below but effective 9/1/2015, all materials (except for the SCID and KSADS) must

be uploaded using the Add button above.

View: 2.09 - 2.10

Section 2 - Research Design and Methods

2.9 If subjects are also patients, will any clinical procedures that are being used for their conventional medical care also be used for research purposes?

* yes

If Yes, describe the clinical procedures (and, if applicable, their frequency) that will be used for research purposes:

Information contained in their electronic medical record related to their qualifying diagnosis and swallowing difficulty will be accessed for this research. Specifically, MBS evaluations will be accessed/reviewed as part of the assessment process for the specific aims of this research.

2.10 The blood sample question was moved to 2.6.1.

View: 2.11

Section 2 - Research Design and Methods

2.11 What is the total duration of the subject's participation in this research study across all visits, including follow-up surveillance?

* Approximately 8 weeks for IOPI plus standard therapy. Approximately 16 weeks for the crossover group.

View: 2.12

Section 2 - Research Design and Methods

2.12 Does this research study involve any type of planned deception?

If Yes, you are required to request an alteration of the informed consent process (question 4.7)

* No

2.12.1 Describe the planned deception:

*

2.12.2 Provide a justification for this planned deception:

*

2.12.3 Describe when and how subjects will be debriefed:

*

View: 2.13 HB

Section 2 - Research Design and Methods**2.13 Does this research study involve the use of UPMC/Pitt protected health information that will be de-identified by an IRB approved "honest broker" system?**

* No

2.13.1 Identify the name of the honest broker system:**2.13.2 Specify the IRB-assigned honest broker system number (e.g., HB123456):****2.13.3 Specify the names of the individuals who will provide the honest broker services:**

Last	First	Organization
------	-------	--------------

There are no items to display

Previous inputted information for Question 2.13.3:**2.13.4 Upload the signed honest broker assurance agreement:**

Name	Modified Date
------	---------------

There are no items to display

View: 2.14

Section 2 - Research Design and Methods**2.14 Will protected health information from a UPMC/Pitt HIPAA covered entity be accessed for research purposes or will research data be placed in the UPMC/Pitt medical record?**

* Yes

If you answer **Yes**, you are required to submit this study to the Center for Assistance in Research using e-Record (CARe). Per UPMC Policy HS-RS0005, all research projects that access or involve UPMC electronic protected health information (e- PHI) must be submitted to CARe, with the exception of clinical trials that are contracted through the UPMC Office of Sponsored Programs and Research Support (OSPARS).

Complete the online submission form at <https://care.upmc.com/request.aspx>. After the study is submitted in OSIRIS, a CARe representative will conduct a review. You will be notified once your CARe review is complete or if anything further is needed.

Studies that will access only paper-based medical records (not in combination with any electronic records) do not need to be submitted to CARe.

For additional information, please see <https://care.upmc.com>.

Describe the medical record information that will be collected from the UPMC/Pitt HIPAA covered entity and/or the research-derived information that will be placed in the medical records.

Information to be collected:

1. site and staging of qualifying head/neck cancer.
2. modified barium swallow video data
3. medical history of pneumonia, feeding tubes
4. patient age and gender, date of completion or cancer treatment, type of chemotherapy and total radiation therapy dosage

Research information to be placed into medical records would include:

1. Outcomes of therapy (including IOPI results/tongue strength)
2. Changes of research outcome measures pertinent to patient clinical care.
3. Type of exercise regimen the participant used.

2.14.1 Will protected health information from a non-UPMC/Pitt HIPAA covered entity be obtained for research purposes or will research data be placed in the non-UPMC/Pitt medical record?

* No

If Yes, describe how the HIPAA requirements will be met:

I, [name] , certify that any member of my research team accessing, reviewing and/or recording information from medical records have completed the CITI Privacy & Information Security course or, if completed within the past year, the Internet-Based Studies in Education and Research (ISER) HIPAA for Researchers (Formerly RPF Module 6). The HIPAA certificates must be available for review if audited but do not need to be uploaded into this OSIRIS application.

* Yes

2.14.2 Are you requesting a waiver of the requirement to obtain written HIPAA authorization for the collection of the PHI?

* No

View: 2.15

Section 2 - Research Design and Methods**2.15 Does this research study involve the long-term storage (banking) of biological specimens?**

* No

2.15.1 Broadly describe the intended future use of the banked biological specimens:**2.15.2 Indicate the planned length of storage of the banked biological specimens:**

*

2.15.3 Will biological specimens be stored **without identifiers or linkage codes?**

If you answer Yes, the samples will not be stored with any identifiers or linkage codes and it is highly unlikely to be linked back to the individual.

If you answer No, the samples will be stored with an identifier or linkage code and can be linked back to the individual.

*

View: 2.16

Section 2 - Research Design and Methods

2.16 **Will research participants be asked to provide information about their family members or acquaintances?**

* No

2.16.1 **Describe what information about the third party will be obtained from the participant:**

2.16.2 **If the information about the third party is of a private nature, can the identity of the third party be readily ascertained or associated with this information?**

*

Describe the **private information** that will be collected and recorded about the third party:

View: 2.17 - 2.18

Section 2 - Research Design and Methods

2.17 **What are the main outcome variables that will be evaluated in this study?**

1. Tongue pressure generation (strength).
2. Airway protection during swallowing (penetration-aspiration scale score of MBS data).
3. Pharyngeal residue after swallowing (pharyngeal retention scale rating of MBS data).
4. Swallowing impairment based on EAT-10, VAS, FOIS.
5. Swallow kinematic measures of MBS data on a swallow by swallow basis (videofluoroscopic image analysis with image processing software):
 - a. oral transit duration (duration of bolus transit through the oral cavity)
 - b. stage transition duration (measure of pharyngeal onset delay time)
 - c. duration of impaired oral containment (measure of bolus control in the oral cavity)
 - d. pharyngeal transit duration (duration of bolus transit from oral cavity to inferior pharynx)
 - e. pharyngeal response duration (duration of hyoid bone maximal movement during the swallow)
 - f. duration of upper esophageal sphincter opening
 - g. laryngeal closure duration (duration of airway closure)
 - h. we may analyze the magnitude of epiglottic inversion (rotation of the epiglottis during swallows which relates to laryngeal closure)

- i. we may analyze the magnitude of hyoid displacement (distance traveled by the hyoid bond during swallows)

2.18 Describe the statistical approaches that will be used to analyze the study data.

* Addressed below:

We will perform t-tests to compare the dependent variable values from each measure (penetration-aspiration scores, pharyngeal retention scores, swallow kinematic measures, tongue pressure scores, EAT-10 scores, VAS scores, and patient weight. We may also perform ANOVAs and post hoc analyses to determine the main effect of treatment condition on the dependent variables, and to determine the presence of any interaction effects, and single subject analyses using the C statistic, to determine individual effect sizes for individual participants. Analyses will be designed to compare performance at the following time points:

1. between groups comparisons at time 1 (start of treatment) and at 2 (end of treatment) to evaluate differences between groups at the start and end of 8 weeks of therapy.
2. within groups comparisons between time 1 and 2 (standard therapy vs. standard therapy + IOPI) to evaluate the magnitude of differences from beginning to end of therapy.
3. within group comparison (standard treatment crossover only) at time 1 and time 3 (8 weeks after crossover of standard treatment subjects into standard therapy + IOPI) to evaluate the magnitude of differences from beginning of therapy to end of second phase of therapy (combined standard therapy, with crossover to standard + IOPI).

View: 2.19 - 2.19.6

Section 2 - Research Design and Methods

2.19 Will this research be conducted in (a) a foreign country and/or (b) at a site (e.g., Navajo Nation) where the cultural background of the subject population differs substantially from that of Pittsburgh and its surrounding communities?

* No

Note that copies of training records, licenses, certificates should be maintained in the study regulatory binder and are subject to audit by the Research Conduct and Compliance Office (RCCO).

In addition, individuals planning to conduct human subject research outside the United States must complete an optional module on the CITI training website: International Studies. [Click here](#) to access the instruction sheet for accessing optional CITI modules.

2.19.1 Address the following for each of the foreign/culturally different sites where this research will be conducted:

- Name of site
- Name of authorized individual (e.g., IRB Chair) from the local IRB or other human subject protections entity that is responsible for the review and approval of the project; upload approval letter with an English translation, if applicable
- Name and qualifications of the site collaborator responsible for the conduct of the research (e.g., site PI)
- The anticipated number of subjects that will be enrolled at that site
- If Federally funded, provide the Federalwide Assurance number (FWA) assigned to the site

*

Site	Date Modified
------	---------------

There are no items to display

2.19.1.1 Provide a description of the context of cultural norms and local laws and highlight differences between U.S. culture in all areas relevant to your study, including, at a minimum:

- Age of majority of participants to be enrolled
- If study includes minors or decisionally impaired subjects, summarize laws on guardianship
- If your study involves any invasive medical procedure (including blood draws), provide assurance that the individuals undertaking those procedures for research purposes are appropriately credentialed.
- If your study involves the administration of a drug, device or biologic for research purposes, describe the process for shipping, labeling, storing and dispensing, and indicate how these are consistent with all relevant local (and US) laws, including those requiring import / export permits.
- If your study involves collection of biological specimens, describe the process for shipping, labeling, storing and using such samples. Identify any special local consent requirements, and any special permits that may be required by local law.

*

2.19.1.2 **Describe any aspects of the local cultural, political or economic climate that might increase the risks of harm for either local participants or researchers. Describe the steps you will take to minimize these risks. UPitt Faculty, Staff, and Students must access the **Travel Registry** page. Go to my.pitt.edu and the link is displayed under My Resources.**

*

2.19.2 **Will all individuals being recruited to participate in this research study be able to read and comprehend English**

*

If **No**, describe how consent will be obtained. Explain provisions for culturally appropriate recruitment and consent accommodations such as, translations or involvement of native language speakers, especially if literacy is not widespread in this country.

2.19.2.1 **If translated documents are used, upload a signed translator certification form and back translations (if applicable):**

(Translator Certification Form is available under the **Resources** tab located to right of this item)

Name Modified Date

There are no items to display

2.19.3 **Will all of the research procedures described in this IRB application be conducted at the foreign/culturally different sites?**

* Yes No

If **No**, describe the subset of research procedures to be performed at the sites:

2.19.4 **To what extent do the local site requirements to protect subject confidentiality and privacy differ from US standards. If applicable, explain how those will be addressed by this research team:**

*

2.19.5 **If the researcher is a student, describe how the student will communicate with the advisor during the conduct of the research and how the advisor will oversee the research:**

View: 2.21

Section 2 - Research Design and Methods

2.21 **Will this research study be conducted within a nursing home located in Pennsylvania?**

* No

2.21.1 **Does this research involve a medical procedure or an experimental treatment?**

*

2.21.2 **Does the research study involve the exposure of nursing home residents to pain, injury, invasion of privacy, or ask the resident to surrender autonomy?**

*

If **Yes to either question**, upload the Pennsylvania Department of Health approval letter. 28 PA Code Section 201.29 (o) specifies that prior to the initiation of research, and in addition to IRB approval, any study that includes experimental research or treatment conducted in a nursing home must be approved by the Pennsylvania Department of Health. A signed consent form from nursing home resident-subject is also required.

Name Modified Date

View: 3.01 - 3.04(a)

Section 3 - Human Subjects

3.1 **What is the age range of the subject population?**

18 and older

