Once enrolled through written informed consent, research participants will be assigned to either "standard therapy" or to "standard therapy with IOPI" treatment group by a clinical investigator. This assignment will be in an alternating fashion based on date of enrollment. IOPI treatment consists of 10 repetitions of the IOPI exercises, three times a day on three days per week for 8 weeks. It will take 30 minutes to train the subject on how to do the exercises and record them and that it takes 5-10 minutes to complete 30 repetitions of the exercise. Subjects will be completing a diary related to their exercise regimen.

Subjects will undergo a standard of care modified barium swallow study by clinical staff prior to the onset of therapy to obtain baseline measurements of airway protection and oropharyngeal kinematic function. They will also be asked to complete a Visual Analog Scale (VAS) to rate their dysphagia prior to initiation of therapy, therapy by marking an "X" on a 100mm line indicating their perception of the severity of their dysphagia (0 = least severe, 100 = most severe). They will also be asked to complete a dietary assessment tool/questionnaire consisting of 10 items (EAT-10). Tongue isometric pressure generation (strength) will be measured with the IOPI. This requires the subject to press a small plastic air-filled bulb between the tongue and hard palate, which transfers isometric pressure on the IOPI. The Functional Oral Intake Scale (FOIS) will be used by the clinician to rate current level of oral intake. Finally subjects will be weighed.

Approximately 8 weeks after the initiation of therapy ("standard" or "standard w/ IOPI") individuals will be asked to complete the VAS and the EAT-10, and the clinician will repeat the FOIS and weigh the subjects, once again at their 8-week standard of care clinical follow up visit. 8 weeks is the usual standard of care follow up visit. A modified barium swallow (MBS) test will also be performed as part of standard of care at about the 8 week time point (after therapy). Finally isometric pressure (tongue strength) will be measured at this point.

At 8 weeks, individuals who were assigned to the "standard therapy only" group, who still require swallowing therapy, will be asked if they would like to add the IOPI to their therapy

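### Section 2.18 does not say which ANOVA term carries the treatment conclusion; if the model is treatment by time, the main effect it names is half the week-8 effect

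*Combined protocol and SAP*

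**What the plan says.** Section 2.18 makes one firm commitment: "We will perform t-tests to compare the dependent variable values from each measure". The ANOVA is optional: "We may also perform ANOVAs and post hoc analyses". The sentence gives it two purposes. The first is the main effect of treatment condition: "ANOVAs and post hoc analyses to determine the main effect of treatment condition on the dependent variables". The second is "and to determine the presence of any interaction effects".

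The section then lists three sets of comparisons: between groups at time 1 and at time 2; within each group from time 1 to time 2; and a "within group comparison (standard treatment crossover only) at time 1 and time 3".

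It does not name the ANOVA factors, say whether visit is a repeated factor, identify the interaction, or say which term decides whether IOPI helped. Section 2.6 places the baseline swallow study "prior to the onset of therapy to obtain baseline measurements of airway protection and oropharyngeal kinematic function", and has the other baseline measures taken at that point too.

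**The concern.** An ANOVA with an interaction has at least two factors, and the only ones that 2.18 itself describes are treatment and time. On that reading, the term that the section ties to treatment condition is an average over two visits. Therapy cannot have had any effect at the first of them. The term that isolates the effect of adding IOPI is arm-by-time, which the section covers only by a general reference to interactions.

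If such an ANOVA were run and its main effect reported as the treatment effect, two things could go wrong. A real benefit would appear at about half its size and could easily miss significance. A chance difference between arms at baseline would carry into the estimate and could be read as benefit or harm. The t-test at time 2 and the ANOVA could also disagree on the same data, and the plan has no rule for which one counts.

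**Working it through.** **Inputs from the documents.** 50 subjects per group (section 3.11); time 1 before therapy (section 2.6); time 2 at about 8 weeks (sections 2.6 and 2.18).

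**Assumed inputs.** The documents give no alpha, effect size, SD, correlation or dropout. Section 3.12 sets the sample size by referral base and expected recruitment, so there is no power figure to reproduce. I take two-sided alpha 0.05, SD 1 at both visits, no dropout, a true week-8 difference D of 0.5 or 0.8 SD, no true baseline difference, and a baseline-to-week-8 correlation r of 0.3, 0.5 or 0.7.

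**Step 1: what each term estimates.** Write B for the arm difference at time 1 and W for the arm difference at time 2. In a balanced two-visit arm-by-time ANOVA:

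- Main effect of arm = (B + W)/2. With B = 0 and W = D this is D/2, or 0.25 SD when D = 0.5.
- Arm-by-time term (difference in change) = W − B = D, or 0.50 SD.

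A baseline difference of 0.3 SD with no treatment effect adds 0.3/2 = 0.15 SD to the main effect from the time 1 visit alone. If it carries over to time 2 in proportion to r, the total is 0.3 × (1 + r)/2 = 0.20/0.23/0.26 SD at r = 0.3/0.5/0.7.

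**Step 2: standard errors with n = 50 per arm.**

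- Main effect: √[((1 + r)/2) × (2/50)] = 0.161/0.173/0.184 at r = 0.3/0.5/0.7
- Arm-by-time: √[2(1 − r) × (2/50)] = 0.237/0.200/0.155
- t-test at time 2: √(2/50) = 0.200
- Time 2 adjusted for time 1 (ANCOVA): √[(1 − r²) × (2/50)] = 0.191/0.173/0.143

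**Step 3: power** (noncentral t, 98 df; 97 for ANCOVA).

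| Term | Estimate when D = 0.5 | r = 0.3 | r = 0.5 | r = 0.7 |
|---|---|---|---|---|
| Main effect of arm | 0.25 SD | 34% | 30% | 27% |
| Arm-by-time | 0.50 SD | 55% | 70% | 89% |
| t-test at time 2 | 0.50 SD | 70% | 70% | 70% |
| ANCOVA at time 2 | 0.50 SD | 74% | 82% | 93% |

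At D = 0.8 the main effect has 69/63/57% and the time-2 t-test 98%.

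**Step 4: check by simulation** (20,000 trials, D = 0.5, r = 0.5). The mean main effect was 0.2505 and the mean arm-by-time term 0.5012. Power was 30% for the main effect, 70% for arm-by-time and 70% for the time-2 t-test, in agreement with the formulas.

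**The case against.** The strongest reply is that the plan does not commit to the faulty analysis. Most of it stands.

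- **The ANOVA is optional.** The t-test between groups at time 2 is what will be done, and it contains no pre-therapy data. A reader might infer that the trial would miss an effective add-on because of the ANOVA wording. The documents do not support that.
- **Interactions are in the same sentence.** It would be wrong to say that the ANOVA is aimed at the main effect alone. If arm-by-time is among the interactions meant, the right term is already tested. What remains is that the section does not name it or say that it decides.
- **The factors are inferred.** Section 2.14 collects tumour site, stage, chemotherapy type and radiation dose, and treatment could be crossed with one of these at time 2. That model has an interaction, and its treatment main effect is not halved by a baseline visit. A one-way ANOVA on time-2 values or on change scores also avoids the halving, though it has no interaction. Treatment by time fits the section best, but it is not stated.
- **No listed comparison averages the visits.** True, and this weakens the averaging reading. But the same list, by time point, is why time is the obvious second factor.
- **Time 3.** A reader might infer that time 3 would enter a three-visit model, or be coded as the IOPI condition. Section 2.18 proposes neither; it confines time 3 to a within-group comparison in crossover subjects.
- **The loss depends on the assumed effect.** At 0.8 SD the main effect has 57 to 69% power, so one cannot say that an effective add-on would usually look non-significant.

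**Conclusion.** The point holds in a limited form. Section 2.18 leaves the ANOVA model and the deciding term open, and the one treatment term that it names is the wrong one under the most natural model. There, the main effect is half the week-8 difference plus half of any baseline difference. Exact halving needs two equally weighted visits and no baseline difference. The power loss shown rests entirely on assumed inputs: under a 0.5 SD effect, about 30% against 70% for arm-by-time at r = 0.5.

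This goes beyond missing detail, because a better estimator is available from data already collected. It remains a matter of an optional supporting analysis in a pilot, and it does not undermine the committed comparison at time 2.

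**What to change.** Replace the ANOVA wording in section 2.18 with:

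*The between-arm treatment effect will be estimated at time 2 with adjustment for the time 1 value (ANCOVA), reported with its 95% CI. If a repeated-measures ANOVA over times 1 and 2 is also run, the treatment effect is the arm-by-time term, and the main effect of arm will not be interpreted as the treatment effect. Time 3 data are used only in comparison 3.*

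ANCOVA comes first because under the assumptions above it has more power than the arm-by-time term and the time-2 t-test at every correlation shown. At r = 0.3 the arm-by-time term (55%) falls below the t-test (70%), so it should not be the only replacement. The t-tests can stay, and so can post hoc comparisons following an interaction, which are ordinary practice. A classical repeated-measures ANOVA uses only subjects with both visits, so the number analysed should be reported with it.

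The cost is a change of wording in one section, with no new data, visits or patients.

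### Section 2.18 names no baseline-adjusted between-arm comparison although time 1 values are collected, and it lists no test for FOIS, a main outcome

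*Combined protocol and SAP*

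**What the plan says.** Section 1.2 sets a between-arm aim: standard exercise plus IOPI against standard exercise alone.

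Section 2.18 says that t-tests will be done on a list of measures. The list opens with penetration-aspiration scores and continues with "pharyngeal retention scores, swallow kinematic measures, tongue pressure scores, EAT-10 scores, VAS scores, and patient weight". Three comparisons follow:

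- Comparison 1 is "between groups comparisons at time 1 (start of treatment) and at 2 (end of treatment) to evaluate differences between groups".
- Comparison 2 is "within groups comparisons between time 1 and 2 (standard therapy vs. standard therapy + IOPI) to evaluate the magnitude of differences".
- Comparison 3 is within the crossover subset only, time 1 against time 3.

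A further analysis is optional: "We may also perform ANOVAs and post hoc analyses to determine the main effect of treatment condition on the dependent variables". The same sentence mentions interaction effects but names no factors. No section mentions a covariate, ANCOVA or baseline adjustment.

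The baseline values are planned. Section 2.6 has a modified barium swallow "prior to the onset of therapy to obtain baseline measurements of airway protection and oropharyngeal kinematic function", and VAS, EAT-10, tongue pressure, FOIS and weight are also taken before therapy. All are repeated at about 8 weeks.

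FOIS is a main outcome in section 2.17, item 4: "Swallowing impairment based on EAT-10, VAS, FOIS". Section 2.6 has it rated at the start ("The Functional Oral Intake Scale (FOIS) will be used by the clinician to rate current level of oral intake") and again at 8 weeks ("the clinician will repeat the FOIS and weigh the subjects"). It is not in the 2.18 list. Weight is in that list but is not among the 2.17 main outcomes.

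**The concern.** The aim is a difference between arms. The one between-arm outcome test that 2.18 clearly commits to uses the week-8 values alone and leaves the patient's own starting value unused. Section 3.12 says that enrolment was set by the referral base and realistic recruitment, so recruiting more patients is not an easy route to precision. Adjusting for a value already collected is. It also removes, under a linear model, the part of the week-8 difference that comes from measured baseline imbalance. Section 2.18 plans a between-arm look at time 1 but does not say what follows if the arms differ there.

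The wording of comparison 2 adds a second difficulty: two analysts could take different treatment comparisons from the same section. The FOIS omission is a separate mismatch between 2.17 and 2.18 and depends on no assumed figure.

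**Working it through.** **Text check.** Of the three comparisons, one is labelled between groups. Baseline-adjusted between-arm comparisons named: none. Tests listed for FOIS: none.

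**No plan figure to reproduce.** Section 3.11 gives 50 per arm, and 50 + 50 = 100 agrees with section 3.10. Section 3.12 gives no alpha, power, target effect, SD, correlation or dropout.

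**Inputs.** From the documents: 50 per arm. Assumed: two-sided 0.05, 80% power, no dropout, normal outcomes, and a correlation rho between time 1 and week 8 of 0.1 to 0.8. Differences are in units of the week-8 SD.

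**Variance factor V**, relative to the unadjusted week-8 test:

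- Unadjusted: V = 1, 98 df.
- ANCOVA: V = (1 − rho²)(1 + 1/96), 97 df. The second term is the cost of estimating the slope, with 96 = 2 × 50 − 4.
- Change score with equal SDs at both visits: V = 2(1 − rho), 98 df.

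**Detectable difference.** This was solved from the noncentral t distribution. It is very close to (t0.975 + t0.80) × √(2V/50). Unadjusted: (1.984 + 0.845) × 0.20 = 0.566 SD. At rho = 0.5, ANCOVA has V = 0.75 × 1.0104 = 0.758, and 0.566 × √0.758 = 0.493 SD.

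| rho | Unadjusted | ANCOVA | Change score, equal SDs |
|---|---|---|---|
| 0.1 | 0.566 | 0.566 | 0.759 |
| 0.2 | 0.566 | 0.557 | 0.716 |
| 0.3 | 0.566 | 0.543 | 0.670 |
| 0.5 | 0.566 | 0.493 | 0.566 |
| 0.7 | 0.566 | 0.406 | 0.438 |
| 0.8 | 0.566 | 0.341 | 0.358 |

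The 95% CI half-width, t0.975 × √(2V/50), is 0.397 SD unadjusted. With ANCOVA it is 0.381 / 0.346 / 0.285 / 0.239 SD at rho 0.3 / 0.5 / 0.7 / 0.8.

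**Where the gain vanishes.** ANCOVA's V equals 1 when (1 − rho²) × 97/96 = 1, that is rho² = 1/97, or rho of about 0.10. Below that the covariate costs slightly more than it returns, by at most about 1% of the variance.

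**Change score with unequal SDs.** Let k be the baseline SD divided by the week-8 SD. The change score has V = 1 + k² − 2 rho k = (1 − rho²) + (k − rho)². This is never below 1 − rho², and it equals it when k = rho. At k = 0.7 and rho = 0.7, V is 0.510 for change against 0.515 for ANCOVA, and the detectable differences are 0.404 and 0.406 SD: a tie. ANCOVA is therefore essentially never worse than change. It is clearly better when the SDs are equal.

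**The case against.** The best reply is that comparison 2 may already be a between-arm comparison of change. Its parenthesis sets one arm against the other and it speaks of the magnitude of differences over therapy; the within-groups label could be the slip. The optional ANOVA could likewise carry an arm-by-visit term. This stands as far as it goes: a reader should not infer that an unadjusted week-8 test is certainly the sponsor's only intended treatment comparison. But the first is ambiguous and the second is optional with no factors named. With two visits, either would give at most a change-score contrast, which is not adjustment for baseline.

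A pilot with no stated power target also cannot fail one. That is fair: the 80% power figures only illustrate size. At a correlation of 0.2 or below there is almost nothing to gain, and the normal-theory figures do not describe the ordinal ratings, including FOIS.

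Three stronger readings are tempting, and the documents do not support them:

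- A reader might infer that the planned t-test is invalid. It is not, if assignment is as good as random.
- A reader might infer that adjustment repairs the assignment method. Section 2.6 has a clinical investigator assign patients alternately by enrolment date. Adjustment does not cure selection arising from a predictable sequence. If the arms differ systematically at baseline, ANCOVA and change scores can disagree, and precision alone does not settle which to believe.
- A reader might infer that within-arm p-values will be taken as evidence of a treatment effect. No section says so.

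The FOIS gap may be a drafting slip, since the list's parenthesis is never closed. It still needs correcting, and it adds no weight to the argument for adjustment.

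**Conclusion.** The point holds as a recommended improvement, not as an error. Section 2.18 leaves the baseline values out of the between-arm comparison, words comparison 2 so that it can be read two ways, and omits FOIS. The first two points hold on every reading of comparison 2 and of the optional ANOVA.

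In size, adjustment is worth nothing at a correlation near 0.1, little at 0.3 (0.57 to 0.54 SD) and a material amount from about 0.5 (0.57 to 0.49 SD, reaching 0.34 SD at 0.8). These figures rest on 50 per arm from section 3.11 and on the assumptions listed above. The clear margin over a change score also needs equal SDs at the two visits. Confidence is high on the absence of adjustment and of FOIS, and moderate on what comparison 2 was meant to be.

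**What to change.** In section 2.18:

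1. State the between-arm comparison for each outcome as the week-8 value compared by arm, adjusted for the patient's own time 1 value. Use ANCOVA for tongue pressure, EAT-10, VAS, weight and the kinematic measures. Section 2.17 takes the kinematic measures swallow by swallow, so define one summary per patient first. Report the adjusted difference with a 95% CI.
2. Reword comparison 2 so that it is clearly within-arm and descriptive.
3. Add FOIS to the analysed measures, with a baseline-adjusted analysis suited to an ordinal scale.

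The cost is wording and slightly more analysis work, with no new visit or measurement. Each ANCOVA spends one degree of freedom. Patients without a time 1 value drop out of the adjusted model, so 2.18 should say how they are handled.
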